#### 10.4.2. Secondary Objective:

**Feasibility & Safety:** One important secondary objective is to evaluate the feasibility and safety of obtaining multiple tissues and biofluids in an individual with PD. Feasibility will be assessed by tabulating the percentage of subjects in each group who provide complete samples. The assessment of safety will be based primarily on the frequency of procedure related AEs. All AEs will be coded using the Medical Dictionary for Regulatory Authorities (MedDRA). Procedure related AEs will be summarized by system organ class and preferred term. We will examine safety across groups in two different ways. First, the percentage of subjects who experience any procedure related AEs will be compared across groups using a chi-square test. Additionally, the rates of procedure related AEs will be compared using a Generalized Linear Model with a Poisson link.

**Compare**  $\alpha$ -syn Load Across PD Groups: Another important secondary objective is to compare the  $\alpha$ -syn load among the tissues and fluids in the PD cohort subdivided by the clinical stage of disease (early PD not requiring dopamine replacement therapy, moderate PD on

dopamine replacement therapy without motor fluctuations, advanced PD with motor fluctuations). To address this objective, trend tests (continuous or categorical, as appropriate) will be performed to assess  $\alpha$ -syn levels across the three cohorts of PD subjects.

**Compare**  $\alpha$ -syn Load with DAT Imaging: Another important secondary objective is to compare the  $\alpha$ -syn load among the tissues and fluids with disease severity based on striatal degeneration measured by DAT imaging across the PD groups in addition to comparing PD and HC groups. To accomplish this objective, each measure of  $\alpha$ -syn load will be correlated with DAT imaging data using an appropriate Generalized Linear Model.

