# 3. STUDY DESIGN

# 3.1. Overall Study Design

This is a multi-center, cross-sectional, observational study to evaluate  $\alpha$ -syn pathology in multiple tissues and biofluids in individual subjects with PD and HC at a single time point. Each subject's participation will be approximately 16 weeks. The total duration for sample collection for this study will be approximately 24 months. Analysis of the samples will occur following collection of the samples.

The study is designed to occur in four visits: Screening Visit, Biofluid Collection and Skin Biopsy Visit, Colon Biopsy Visit and Submandibular Gland Biopsy Visit.

The Screening Visit will include obtaining informed consent prior to the initiation of any procedures followed by procedures to evaluate eligibility (clinical laboratory evaluations, medical history, physical examination, electrocardiography [ECG] and DaTSCAN™ Imaging) for participation, Montreal Cognitive Assessment (MoCA) and clinical characterization of PD (Movement Disorder Society Unified Parkinson's Disease Rating Scale [MDS-UPDRS], Hoehn and Yahr, Schwab and England, SCOPA-AUT). In addition, all subjects will complete a University of Pennsylvania Smell Identification Test (UPSIT). DaTSCAN™ imaging obtained as part of the Parkinson's Progression Markers Initiative (PPMI) study may be utilized for this study if completed within 6 months of the screening visit.

Upon confirmation of eligibility and within 120 days of the Screening Visit (based on the date of initial screening activities if occurs on more than one day), subjects will undergo the remaining visits: Biofluid Collection and Skin Biopsy Visit, Colon Biopsy Visit and Submandibular Gland Biopsy Visit. These visits may occur in an order most convenient for scheduling purposes.

For the Biofluid Collection and Skin Biopsy Visit, subjects will undergo collection of whole blood, serum, and plasma for the level of total  $\alpha$ -syn,  $\alpha$ -syn species and other potential biomarkers. Whole blood sample will also be used for extraction of DNA for genomic analyses and RNA for gene expression analyses. Whole blood sample will also be used for a complete blood count (CBC) and assessment of reticulocytes at a central laboratory. Saliva samples will be obtained using the passive drool collection method and analyzed for  $\alpha$ -syn species levels using

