# **3.3.** Study Population

## 3.3.1. Subject Numbers

Up to 100 subjects will be enrolled in this study. Subjects are considered enrolled in the study if they complete screening and are found to be eligible based on the inclusion and exclusion criteria. The enrollment goal for this study is 80 subjects (20 early PD not requiring dopamine replacement therapy, 20 moderate PD on dopamine replacement therapy without motor fluctuations, 20 advanced PD with motor fluctuations, 20 HC subjects) that complete at least 2 biofluid samplings (blood, saliva and CSF) and at least 2 tissue samplings (skin, colon, submandibular gland).

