# 4.2. Schedule of Activities (See Appendix 1)

# 4.3. Study Procedures by Visit

Subjects will undergo all procedures as outlined in the sections below. Assessments that require completion by the Site Investigator (unless otherwise approved and delegated) include: Neurological exam, MDS-UPDRS Part I, III and IV, Hoehn and Yahr Stage, and PD Stage Assignment.

Specific procedures for the clinical labs, biomic labs, imaging, LP, skin biopsy, colon biopsy and submandibular gland biopsy are provided in the S4 Laboratory Manual.

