### 5.1.15.2. Adverse Events

A clinical AE is any untoward medical occurrence in a subject undergoing procedures as a participant in a clinical trial, without regard to the possibility of a causal relationship. Study site personnel will record the occurrence and nature of each subject's pre-existing conditions. During the study, site personnel will record any change in the condition(s) and the occurrence and nature of any AEs that occur during the reporting periods, which occur 7 days (±2 days) after each of the following procedures: DaTSCANTM, LP, skin biopsy, colon biopsy and submandibular gland biopsy. Site Investigators will document their assessment of the potential relatedness of each AE to study procedures or imaging agent administration via an AE form.

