## **10. STATISTICAL METHODOLOGY**

### **10.1.** Analysis Populations

### 10.1.1. Safety Analysis Population:

All safety analyses will include all subjects who were enrolled and completed at least one sampling procedure (LP, blood draw, saliva collection, skin

biopsy, colonic biopsy, or submandibular gland biopsy) as part of this study. Subjects in this analysis set will only be used for feasibility and safety analyses.

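### The procedure-related AE rate model is misnamed and, fitted as a plain Poisson model, makes no allowance for overdispersion or for subjects having different numbers of procedures

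*Protocol*

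**What the plan says.** Protocol Section 10.4.2 plans two group comparisons of procedure-related AEs. The first is at subject level: "the percentage of subjects who experience any procedure related AEs will be compared across groups using a chi-square test". The second is on event rates: "the rates of procedure related AEs will be compared using a Generalized Linear Model with a Poisson link". The denominator of the rate is not stated, and nothing is said for or against a dispersion parameter, robust errors or an offset.

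Four other places determine how many AEs a subject can contribute:

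- Section 5.1.15.2 ties AE recording to "reporting periods, which occur 7 days (±2 days) after each of the following procedures", and lists five: DaTSCAN, LP, skin biopsy, colon biopsy and submandibular gland biopsy. Section 6.1 lists the same five. Blood draw and saliva collection have no AE period of their own.
- Section 10.1.1 defines the safety set as "all subjects who were enrolled and completed at least one sampling procedure". A blood draw or saliva collection is enough.
- Section 3.3.1 sets the enrolment goal as subjects who "complete at least 2 biofluid samplings (blood, saliva and CSF) and at least 2 tissue samplings (skin, colon, submandibular gland").
- Section 3.1 says that a PPMI scan "may be utilized for this study if completed within 6 months of the screening visit".

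Against these, Section 4.3 sets one schedule for everyone: "Subjects will undergo all procedures as outlined in the sections below".

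**The concern.** Two separate things can go wrong with this model.

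The first is variance. The name of the model contains a slip, since the usual link for a Poisson model is the log. The substance is the Poisson assumption that variance equals mean. AEs from several invasive procedures in one person are unlikely to be independent events at a common rate, because some people bruise, faint or report more than others. That pushes the variance above the mean, and a model that ignores it gives standard errors that are too small.

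The second is exposure. AE observation runs in a window after each procedure, so a subject who has fewer of the five procedures has fewer chances to record an AE. If completion differs between groups, a per-subject rate mixes the risk of the procedures with how many were done. The chi-square test on any AE has the same feature.

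At stake is the reading of the safety comparison across the three PD stages and the healthy controls, which is one stated aim of sampling multiple sites in one individual.

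**Working it through.** The protocol gives no AE rate, dispersion or completion rate by group, so there is no planned figure to reproduce. What follows is a sensitivity calculation. The group size of 20 is from Section 3.3.1. The 0.05 level is borrowed from Section 10.5, which states it only for the CSF sample size. All dispersion and risk values are assumed.

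**Overdispersion.** Let variance = φ × mean.

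- The true standard error is √φ times the Poisson one, so a nominal 95% interval covers 2Φ(1.96/√φ) − 1.
- The four-group likelihood-ratio test has 3 degrees of freedom and a 5% critical value of 7.815. Its actual rejection rate with equal true rates is about P(χ²₃ > 7.815/φ).

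| φ | SE ratio √φ | Coverage of 95% interval | Two-group test | Four-group test |
|---|---|---|---|---|
| 1 | 1.00 | 95% | 5% | 5% |
| 1.5 | 1.22 | 89% | 11% | 16% |
| 2 | 1.41 | 83% | 17% | 27% |

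Simulations of four groups of 20 with negative-binomial counts agree: 15–16% at φ = 1.5 and 27–29% at φ = 2.

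**Range of exposure among evaluable subjects.**

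- Most: scan, LP, skin, colon and gland = 5.
- Fewest with a study scan: blood and saliva meet the biofluid requirement without an LP, so scan plus two tissues = 3.
- Fewest with a reused PPMI scan: two tissues = 2. This rests on an inference that an earlier scan's seven-day window normally falls outside this study.
- In the safety set, a subject with a reused scan and only a blood draw would have 0.

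**Effect of unequal exposure.** With equal risk r per procedure and no offset, the expected rate ratio is the ratio of mean procedures: 4/5 = 0.80, or 20% lower; 5/5 = 1.00, no bias.

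Rejection for two groups of 20 averaging 4 and 5 procedures, with φ = 1:

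- At r = 0.2, expected totals are 20 × 4 × 0.2 = 16 and 20 × 5 × 0.2 = 20. The log ratio is ln 0.8 = −0.223, its SE is √(1/16 + 1/20) = 0.335, and z = 0.67, which gives about 10% rejection.
- At r = 0.4, the totals are 32 and 40, the SE is 0.237 and z = 0.94, which gives about 16%.
- Simulation at r = 0.2 gave 9.9% without an offset and 4.7% with log(number of procedures) as offset.

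**The companion test.** Under the same assumptions (r = 0.2, Poisson), the chance of any AE is 1 − e^(−1.0) = 63% with five procedures and 1 − e^(−0.8) = 55% with four. The chi-square test avoids the Poisson variance assumption but does not correct for exposure.

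**The case against.** The strongest reply is that a protocol may name a model class and leave the offset and dispersion handling to the SAP, which is not at hand. A generalized linear model can carry both, and the word rate implies some denominator. That stands as far as omission goes: the absence of an offset from one sentence is not in itself a fault. It does not cover what the sentence states, which is a model named wrongly and a distribution whose default variance is doubtful for these data.

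A reader might infer that the intervals will be too narrow and that some group will look safer than it is. The documents do not support that. Nothing in them shows overdispersion, and at φ = 1 the Poisson model is correct. All groups share one schedule, and SPECT imaging and LP are planned for every subject (Sections 5.1.8 and 5.1.10). People who cannot safely have the LP or a biopsy are excluded from every group (Section 3.3.4). With equal completion the exposure bias is zero. A larger gap, such as 3 against 5 procedures, would need one group near the evaluable minimum for a study scan while another completes everything, and nothing suggests this.

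A reader might also infer that a per-subject rate is the wrong measure. It is not. The objective concerns sampling an individual, and AEs per participant is a legitimate measure of that burden. An offset on the procedure count has its own weakness: it treats a scan, an LP and a gland biopsy as equal in risk, and it is undefined for a subject with none. It should not replace the per-subject rate.

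Finally, the protocol has partial safeguards. The chi-square test does not rely on Poisson variance, and complete sampling is tabulated by group, so uneven completion would be visible beside the safety results.

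**Conclusion.** The point holds in a conditional form. The model is misnamed, and read plainly it assumes variance equal to mean for counts where that is doubtful. If the counts are overdispersed, the four-group test can reject in about 16% (φ = 1.5) to 27% (φ = 2) of trials against a nominal 5%. The protocol's own rules allow unequal numbers of AE-reporting procedures. If groups differ in completion, the per-subject rate differs for that reason alone, by 20% at 4 against 5, assuming equal risk per procedure. Neither planned comparison corrects for this.

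Whether either condition occurs cannot be known from the protocol, so these figures show what is possible and do not predict the result. Severity is minor: the objective is secondary, the study calls itself exploratory, and no decision rule rests on the test.

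**What to change.** In Section 10.4.2:

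1. Name a Poisson distribution with log link, and state robust standard errors or a negative-binomial model.
2. State that the main rate is per subject.
3. Tabulate procedure-related AEs by procedure type, with the number of subjects who had that procedure as denominator.
4. Report beside the per-subject rate a sensitivity analysis with offset log(number of AE-reporting procedures performed), among subjects with at least one, and note that it treats procedures as equal in risk.

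The cost is a few sentences and routine code. Sections 6.2 and 6.4 already record whether each AE relates to a specific procedure, so no new data are needed. The price is somewhat wider intervals.

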### **10.5.** Sample Size Justification

As this is an exploratory trial, it is difficult to obtain solid estimates for key parameters of interest. However, the PPMI study provides data in an early PD cohort that can be used for the purposes of assessing the "effects" that this study may be powered to detect. In the PPMI cohort of early PD subjects, the mean baseline CSF levels of total  $\alpha$ -syn was equal to  $1845 \pm 770$  pg/ml. With a sample size of 20 subjects per group, and assuming a significance level of 0.05, we will have 80% power to detect a difference of 40% or more between HCs or one of the later PD cohorts versus the early PD cohort. Similarly, the study will have 90% power to detect a difference of 50% or more between HCs or one of the later PD cohort.

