### 10.4. Analysis Plan

#### 10.4.1. **Primary Objective**

The goal of this study is to characterize the distribution of  $\alpha$ -syn pathology through evaluation of quantitative and semi-quantitative outcomes for  $\alpha$ -syn (total, phosphorylated, oligomeric, and other  $\alpha$ -syn species) in multiple tissues and body fluids in individual subjects with clinically typical PD and HC subjects. The primary objectives of the study are to:

- Evaluate the markers of  $\alpha$ -syn as potential surrogate markers for patient selection/enrichment that would be useful in future clinical trials
- Compare  $\alpha$ -syn load in the biofluids and tissues in PD subjects with HC subjects

To address the first objective, the distribution of each  $\alpha$ -syn measurement will be closely examined. The variability of each  $\alpha$ -syn measurement will also be closely examined in an attempt to make recommendations for the optimal measurement to consider in future clinical trials (i.e., the measurement with the lowest variability and, hence, smallest required sample size, to detect clinically important effects of interest).

Two sets of comparisons will be performed to assess the second objective. First, all PD subjects will be pooled and compared to the set of HC subjects with respect to each individual  $\alpha$ -syn measurement. Then, subjects in each of the three separate PD groups will be compared to the healthy controls.

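### The 80% power stated for a later PD cohort versus early PD has no matching planned test when that cohort is the moderate one

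*Protocol*

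**What the plan says.** Section 10.5 sizes the study on total α-syn in CSF, using an external early PD cohort with 1845 ± 770 pg/ml. The setting is "With a sample size of 20 subjects per group, and assuming a significance level of 0.05". The claim is "80% power to detect a difference of 40% or more between HCs or one of the later PD cohorts versus the early PD cohort", so early PD is the reference and healthy controls, moderate PD or advanced PD is the other arm. A second sentence claims "90% power to detect a difference of 50% or more between HCs or one of the later PD cohort" and stops without naming a comparator. The Synopsis carries the same text.

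Section 10.4.1 plans two sets of comparisons: "all PD subjects will be pooled and compared to the set of HC subjects", and then "subjects in each of the three separate PD groups will be compared to the healthy controls". For the objective of comparing load across PD stages, section 10.4.2 says "trend tests (continuous or categorical, as appropriate) will be performed to assess" α-syn levels over the three PD cohorts. The t-tests in section 10.2 concern demographic and clinical characteristics, not α-syn.

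**The concern.** The contrasts used for sizing and the contrasts planned for analysis do not line up. Section 10.5 takes early PD as the reference; section 10.4.1 takes healthy controls. Within PD, the only planned method is a trend test, which looks for an ordered change from early to advanced. Such a test does not answer whether the moderate cohort alone differs from the early cohort, yet the power statement covers either later cohort without condition.

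Comparing load by clinical stage is a named secondary objective. If the trend test is null, a reader of section 10.5 could conclude that a 40% moderate-versus-early difference had been looked for with 80% power. That would be wrong unless advanced PD had moved about as far in the same direction.

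**Working it through.** **Inputs (section 10.5).** Mean 1845 and SD 770 pg/ml (the figure after ± read as an SD), 20 per group, α = 0.05. Assumed because not stated: two-sided test, normal data, common SD, and equally spaced trend scores (-1, 0, 1).

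**Step 1: the stated figures.** A 40% difference is 0.40 × 1845 = 738 pg/ml, or 738/770 = 0.958 SD. The standard error of a difference of two means is 770 × √(2/20) = 243.5. The noncentrality is 738/243.5 = 3.03 on 38 df, which gives 84.0% power. At 50%, 922.5/243.5 = 3.79, which gives 95.8%. The stated 80% and 90% do not reproduce exactly but are on the cautious side for a pairwise t-test. The t-test reaches 80% at a 37.9% difference and 90% at 43.9%.

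**Step 2: which sized contrasts are planned.**

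| Contrast in 10.5 | Planned test of α-syn |
|---|---|
| Healthy controls vs early PD | Yes, pairwise (10.4.1) |
| Advanced vs early PD | No pairwise test; covered in effect by the trend test (10.4.2) |
| Moderate vs early PD | No pairwise test; trend test only |

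**Step 3: what the trend test sees.** With scores -1, 0, 1 and equal groups, the linear contrast is (-1) × early + 0 × moderate + 1 × advanced, that is, advanced minus early. Its standard error is again 243.5, now on 57 df. The moderate mean drops out of the estimate. In a linear regression on stage, a displaced moderate mean also inflates the residual variance, so power is slightly lower.

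**Step 4: power with moderate fixed at +40% of the early mean.**

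| Advanced vs early | Difference (pg/ml) | Noncentrality | Contrast, 57 df | Regression on stage (simulated) |
|---|---|---|---|---|
| 0% | 0 | 0 | 5% | 3% |
| +10% | 184.5 | 0.76 | 12% | 9% |
| +20% | 369 | 1.52 | 32% | 28% |
| +30% | 553.5 | 2.27 | 61% | 58% |
| +40% | 738 | 3.03 | 85% | 83-84% |

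Jonckheere-Terpstra gives about 3%, 8%, 26% and 81% at 0, 10, 20 and 40%. The pairwise moderate-versus-early t-test has 84% in every row.

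**Step 5: is it the sample size or the test?** With only moderate shifted by 40%, an omnibus F test over the three cohorts has 87% power. The shortfall comes from the form of the test, not from 20 per group.

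**The case against.** The strongest reply is that a trend test suits the question. The protocol's rationale (1.2) expects α-syn to track severity. If moderate PD is 40% away from early PD and the pattern is monotone, advanced PD is at least as far away, and the trend test then has 81-85% power or more. That stands, and it limits the point. The power statement carries no such condition, however. The rationale speaks of aggregation rather than total CSF α-syn. The stage definitions also split by treatment and motor complications, and moderate PD has no limit on time since diagnosis.

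It can also be said that the study is exploratory, that 10.5 is an illustration from one marker, and that pairwise follow-up could be set in an SAP that is not shown. This lowers the weight of the point. It does not remove it: the protocol itself names the test for this objective and states power for a different contrast.

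Three stronger readings are tempting, and the documents do not support them:

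- A reader might infer that the trend test has 3-5% power in general. That figure is the non-monotone worst case, with advanced equal to early. There is then no linear trend to find, and rejection near or below α is expected.
- A reader might infer that neither later-versus-early contrast is tested. Advanced versus early is tested in effect, at about the stated power.
- A reader might apply the same criticism to the 90% claim. That sentence names no comparator, so reading it as versus early PD is an inference.

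**Conclusion.** The point holds for the moderate cohort only. The 80% power stated in section 10.5 and the Synopsis is matched by a planned pairwise comparison for healthy controls versus early PD, and in effect by the trend test for advanced versus early. For a 40% moderate-versus-early difference the planned test has the stated power only if advanced PD differs by about 40% as well. Otherwise power falls to 58-61% with advanced at +30%, 28-32% at +20%, and about 3-5% if advanced equals early, against 84% for the pairwise t-test that the sizing implies.

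The result rests on equally spaced scores, a common SD of 770 pg/ml, normal data and a two-sided 0.05 level. Different scores would give the moderate cohort some weight and change these figures. In an exploratory study this is a modest defect, but it is a definite one and worth correcting.

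**What to change.** Preferred: in 10.4.2 keep the trend test and add the moderate-versus-early and advanced-versus-early differences for each marker, reported with confidence intervals. The cost is two more exploratory contrasts per marker, and no extra subjects or procedures.

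Alternative: in 10.5 and the Synopsis, limit the power statement to the comparisons of healthy controls with a PD group and to the early-to-advanced difference tested by the trend. Say that it does not cover a difference confined to the moderate cohort. The cost is about one sentence in each place. Whichever route is taken, name the comparator in the 90% sentence in the same edit.
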